7.1.1.2 CAEPR for tremelimumab

Comprehensive Adverse Events and Potential Risks list (CAEPR) for Tremelimumab (CP-675,206, NSC 744483)

The Comprehensive Adverse Events and Potential Risks list (CAEPR) provides a single list of reported and/or potential adverse events (AE) associated with an agent using a uniform presentation of events by body system. In addition to the comprehensive list, a subset, the Specific Protocol Exceptions to Expedited Reporting (SPEER), appears in a separate column and is identified with bold and italicized text. This subset of AEs (SPEER) is a list of events that are protocol specific exceptions to expedited reporting to NCI (except as noted below). Refer to the 'CTEP, NCI Guidelines: Adverse Event Reporting Requirements' http://ctep.cancer.gov/protocolDevelopment/electronic_applications/docs/aeguidelines.pdf for further clarification. *Frequency is provided based on 1642 patients.* Below is the CAEPR for tremelimumab (CP-675,206).

NOTE: Report AEs on the SPEER **ONLY IF** they exceed the grade noted in parentheses next to the AE in the SPEER. If this CAEPR is part of a combination protocol using multiple investigational agents and has an AE listed on different SPEERs, use the lower of the grades to determine if expedited reporting is required.

Version 2.1, March 25, 2019¹

Adverse Events with Possible Relationship to Tremelimumab (CP-675,206) (CTCAE 5.0 Term) [n= 1642]			Specific Protocol Exceptions to Expedited Reporting (SPEER)
Likely (>20%)	Less Likely (<=20%)	Rare but Serious (<3%)	
BLOOD AND LYMPHATIC SYSTEM DISORDERS			
	Anemia ²		Anemia² (Gr 2)
CARDIAC DISORDERS			
		Myocarditis ³	
ENDOCRINE DISORDERS			
	Adrenal insufficiency ²		
	Endocrine disorders - Other (thyroiditis) ²		
	Hyperthyroidism ²		
	Hypophysitis ²		
	Hypothyroidism ²		
EYE DISORDERS			
	Uveitis		
GASTROINTESTINAL DISORDERS			
	Abdominal pain		Abdominal pain (Gr 2)
	Colitis ²		
Diarrhea			Diarrhea (Gr 2)
		Enterocolitis ²	
		Gastrointestinal disorders - Other (intestinal perforation) ²	
	Nausea		Nausea (Gr 2)
		Pancreatitis ²	
	Vomiting		Vomiting (Gr 2)
GENERAL DISORDERS AND ADMINISTRATION SITE CONDITIONS			
	Edema limbs		Edema limbs (Gr 2)
	Fatigue		Fatigue (Gr 2)
	Fever		Fever (Gr 2)
HEPATOBIILIARY DISORDERS			
		Hepatobiliary disorders - Other (autoimmune hepatitis) ²	
IMMUNE SYSTEM DISORDERS			
		Anaphylaxis	
INJURY, POISONING AND PROCEDURAL COMPLICATIONS			
	Infusion related reaction		
INVESTIGATIONS			
	Alanine aminotransferase increased ²		Alanine aminotransferase increased² (Gr 2)
	Aspartate aminotransferase increased ²		Aspartate aminotransferase increased² (Gr 2)
	Lipase increased ²		Lipase increased² (Gr 2)
	Lymphocyte count decreased ²		Lymphocyte count decreased² (Gr 2)
	Neutrophil count decreased ²		Neutrophil count decreased² (Gr 2)
	Platelet count decreased ²		Platelet count decreased² (Gr 2)
	Serum amylase increased ²		Serum amylase increased² (Gr 2)
	White blood cell decreased ²		White blood cell decreased² (Gr 2)

Adverse Events with Possible Relationship to Tremelimumab (CP-675,206) (CTCAE 5.0 Term) [n= 1642]			Specific Protocol Exceptions to Expedited Reporting (SPEER)
Likely (>20%)	Less Likely (<=20%)	Rare but Serious (<3%)	
METABOLISM AND NUTRITION DISORDERS			
	Anorexia		Anorexia (Gr 2)
	Dehydration		Dehydration (Gr 2)
	Hypokalemia		
		Metabolism and nutrition disorders - Other (diabetes mellitus)	
MUSCULOSKELETAL AND CONNECTIVE TISSUE DISORDERS			
	Arthritis ²		
		Musculoskeletal and connective tissue disorders - Other (Sjogren's syndrome)	
NERVOUS SYSTEM DISORDERS			
		Guillain-Barre syndrome ²	
	Headache ²		
		Myasthenia gravis ^{2,4}	
		Nervous system disorders - Other (encephalitis) ²	
	Peripheral motor neuropathy ²		
	Peripheral sensory neuropathy ²		
RENAL AND URINARY DISORDERS			
	Acute kidney injury		
		Nephrotic syndrome ²	
	Renal and urinary disorders - Other (autoimmune nephritis) ²		
RESPIRATORY, THORACIC AND MEDIASTINAL DISORDERS			
	Cough		
	Dyspnea		
	Pneumonitis ²		
	Respiratory, thoracic and mediastinal disorders - Other (interstitial lung disease) ²		
SKIN AND SUBCUTANEOUS TISSUE DISORDERS			
	Dry skin ²		Dry skin² (Gr 2)
Pruritus			Pruritus (Gr 2)
Rash maculo-papular ²			Rash maculo-papular² (Gr 2)
		Skin and subcutaneous tissue disorders - Other (cutaneous scleroderma-like syndrome)	
		Skin and subcutaneous tissue disorders - Other (Grover's disease)	
	Skin hypopigmentation		Skin hypopigmentation (Gr 2)
	Urticaria ²		
VASCULAR DISORDERS			
		Vascular disorders - Other (giant cell temporal arteritis) ²	

¹This table will be updated as the toxicity profile of the agent is revised. Updates will be distributed to all Principal Investigators at the time of revision. The current version can be obtained by contacting [contact]. Your name, the name of the investigator, the protocol and the agent should be included in the e-mail.

²Immune-related adverse events may occur in any organs including but not limited to the events listed in CAEPR table.

³Myocarditis has been reported with other anti-CTLA4 agents; however, it has not yet been observed in clinical trials of tremelimumab (CP-675,206).

⁴Myasthenia gravis was observed in trials of tremelimumab in combination with durvalumab.

Adverse events reported on tremelimumab (CP-675,206) trials, but for which there is insufficient evidence to suggest that there was a reasonable possibility that tremelimumab (CP-675,206) caused the adverse event:

BLOOD AND LYMPHATIC SYSTEM DISORDERS - Eosinophilia

CARDIAC DISORDERS - Atrial fibrillation; Cardiac arrest

EAR AND LABYRINTH DISORDERS - Tinnitus

ENDOCRINE DISORDERS - Endocrine disorders - Other (Graves' disease with ophthalmopathy)

GASTROINTESTINAL DISORDERS - Constipation; Dyspepsia; Gastritis; Gastrointestinal disorders - Other (diverticulitis); Ileus; Mucositis oral; Rectal hemorrhage

GENERAL DISORDERS AND ADMINISTRATION SITE CONDITIONS - Malaise; Pain; Sudden death NOS

INFECTIONS AND INFESTATIONS - Conjunctivitis; Infections and infestations - Other (oral herpes); Lung infection; Sepsis

INVESTIGATIONS - GGT increased; Weight loss

METABOLISM AND NUTRITION DISORDERS - Hypercalcemia; Hyponatremia

MUSCULOSKELETAL AND CONNECTIVE TISSUE DISORDERS - Arthralgia; Generalized muscle weakness; Myalgia

NERVOUS SYSTEM DISORDERS - Dizziness; Syncope

PSYCHIATRIC DISORDERS - Confusion; Depression; Insomnia

RESPIRATORY, THORACIC AND MEDIASTINAL DISORDERS - Pleural effusion; Respiratory, thoracic and mediastinal disorders - Other (asthma)

SKIN AND SUBCUTANEOUS TISSUE DISORDERS - Alopecia; Hyperhidrosis; Rash acneiform

VASCULAR DISORDERS - Flushing; Hypertension; Thromboembolic event; Vascular disorders - Other (hemorrhage); Vasculitis

Note: Tremelimumab (CP-675,206) in combination with other agents could cause an exacerbation of any adverse event currently known to be caused by the other agent, or the combination may result in events never previously associated with either agent.

7.2 Adverse Events of Special Interest

An adverse event of special interest (AESI) is one of scientific and medical interest specific to

understanding of the Investigational Product and may require close monitoring . An AESI may be serious or non-serious.

AESIs for MEDI4736± tremelimumab include but are not limited to events with a potential inflammatory or immune-mediated mechanism and which may require more frequent monitoring and/or interventions such as steroids, immunosuppressants and/or hormone replacement therapy. “These AESIs may require close monitoring in clinical studies with durvalumab monotherapy and durvalumab combination therapy”. An immune-mediated adverse event (imAE) is defined as an AESI that is associated with drug exposure and is consistent with an immune-mediated mechanism of action and where there is no clear alternate etiology. Serologic, immunologic, and histologic (biopsy) data, as appropriate, should be used to support an imAE diagnosis. Appropriate efforts should be made to rule out neoplastic, infectious, metabolic, toxin, or other etiologic causes of the imAE.

If the Investigator has any questions in regards to an event being an imAE, the Investigator should promptly contact the Study Physician.

AESIs observed with MEDI4736± tremelimumab include:

- Diarrhea / Colitis and intestinal perforation
- Pneumonitis / ILD
- hepatitis / transaminase increases
- Endocrinopathies (i.e. events of hypophysitis/ hypopituitarism, adrenal insufficiency, hyper- and hypothyroidism and type I diabetes mellitus)
- Rash / Dermatitis
- Nephritis /Blood creatinine increases
- Pancreatitis / serum lipase and amylase increases
- Myocarditis
- Myositis / Polymyositis
- Neuropathy / neuromuscular toxicity (e.g. Guillain-Barré and myasthenia gravis) Other inflammatory responses that are rare / less frequent with a potential immune-mediated aetiology include, but are not limited to, pericarditis, sarcoidosis, uveitis and other events involving the eye, skin, haematological and rheumatological events.

In addition, infusion-related reactions and hypersensitivity/anaphylactic reactions with a different underlying pharmacological aetiology are also considered AESIs.

Further information on these risks (e.g. presenting symptoms) can be found in the current version of the durvalumab and tremelimumab Investigator’s Brochures. More specific guidelines for their evaluation and treatment are described in detail in the Dosing Modification and Toxicity Management Guidelines (please see Appendix 1). These guidelines have been prepared by the Sponsor to assist the Investigator in the exercise of his/her clinical judgment in treating these types of toxicities. These guidelines apply to AEs considered causally related to the study drug/study regimen by the reporting investigator..

7.3 Adverse Event Characteristics

- **CTCAE term (AE description) and grade:** The descriptions and grading scales found in the revised NCI Common Terminology Criteria for Adverse Events (CTCAE) version

4.0 will be utilized until March 31, 2018 for AE reporting. CTCAE version 5.0 will be utilized for AE reporting beginning April 1, 2018. All appropriate treatment areas should have access to a copy of the CTCAE version 5.0. A copy of the CTCAE version 5.0 can be downloaded from the CTEP web site

http://ctep.cancer.gov/protocolDevelopment/electronic_applications/ctc.htm.

- **For expedited reporting purposes only:**

- AEs for the agent that are ***bold and italicized*** in the CAEPR (*i.e.*, those listed in the SPEER column, Section 7.1.1) should be reported through CTEP-AERS only if the grade is above the grade provided in the SPEER.
- Other AEs for the protocol that do not require expedited reporting are outlined in section 7.4.4.

- **Attribution of the AE:**

- Definite – The AE *is clearly related* to the study treatment.
- Probable – The AE *is likely related* to the study treatment.
- Possible – The AE *may be related* to the study treatment.
- Unlikely – The AE *is doubtfully related* to the study treatment.
- Unrelated – The AE *is clearly NOT related* to the study treatment.

7.4 Expedited Adverse Event Reporting

7.4.1 Expedited AE reporting for this study must use CTEP-AERS (CTEP Adverse Event Reporting System), accessed via the CTEP Web site (<https://eapps-ctep.nci.nih.gov/ctepaers>). The reporting procedures to be followed are presented in the “NCI Guidelines for Investigators: Adverse Event Reporting Requirements for DCTD (CTEP and CIP) and DCP INDs and IDEs” which can be downloaded from the CTEP Web site (http://ctep.cancer.gov/protocolDevelopment/electronic_applications/adverse_events.htm). These requirements are briefly outlined in the tables below (Section 7.3.3).

In the rare occurrence when Internet connectivity is lost, a 24-hour notification is to be made to CTEP by telephone at [contact]. Once Internet connectivity is restored, the 24-hour notification phoned in must be entered electronically into CTEP-AERS by the original submitter at the site.

7.4.2 Distribution of Adverse Event Reports

CTEP-AERS is programmed for automatic electronic distribution of reports to the following individuals: Principal Investigator and Adverse Event Coordinator(s) (if applicable) of the Corresponding Organization or Lead Organization, the local treating physician, and the Reporter and Submitter. CTEP-AERS provides a copy feature for other e-mail recipients.

7.4.3 Expedited Reporting Guidelines

Use the NCI protocol number and the protocol-specific patient ID assigned during trial registration on all reports.

Note: A death on study requires both routine and expedited reporting, regardless of causality. Attribution to treatment or other cause must be provided.

Death due to progressive disease should be reported as **Grade 5 “Disease progression”** in the system organ class (SOC) “General disorders and administration site conditions”. Evidence that the death was a manifestation of underlying disease (*e.g.*, radiological changes suggesting tumor growth or progression: clinical deterioration associated with a disease process) should be submitted.

Phase 1 and Early Phase 2 Studies: Expedited Reporting Requirements for Adverse Events that Occur on Studies under an IND/IDE within 30 Days of the Last Administration of the Investigational Agent/Intervention ^{1,2}

FDA REPORTING REQUIREMENTS FOR SERIOUS ADVERSE EVENTS (21 CFR Part 312) NOTE: Investigators MUST immediately report to the sponsor (NCI) ANY Serious Adverse Events, whether or not they are considered related to the investigational agent(s)/intervention (21 CFR 312.64) An adverse event is considered serious if it results in ANY of the following outcomes:
 
 1) Death 2) A life-threatening adverse event 3) An adverse event that results in inpatient hospitalization or prolongation of existing hospitalization for ≥ 24 hours 4) A persistent or significant incapacity or substantial disruption of the ability to conduct normal life functions 5) A congenital anomaly/birth defect. 6) Important Medical Events (IME) that may not result in death, be life threatening, or require hospitalization may be considered serious when, based upon medical judgment, they may jeopardize the patient or subject and may require medical or surgical intervention to prevent one of the outcomes listed in this definition. (FDA, 21 CFR 312.32; ICH E2A and ICH E6). 		

ALL SERIOUS adverse events that meet the above criteria MUST be immediately reported to the NCI via electronic submission within the timeframes detailed in the table below.
		
Hospitalization	Grade 1 and Grade 2 Timeframes	Grade 3-5 Timeframes
Resulting in Hospitalization ≥ 24 hrs	10 Calendar Days	24-Hour 5 Calendar Days
Not resulting in Hospitalization ≥ 24 hrs	Not required	

NOTE: Protocol specific exceptions to expedited reporting of serious adverse events are found in the Specific Protocol Exceptions to Expedited Reporting (SPEER) portion of the CAEPR.
 
Expedited AE reporting timelines are defined as:
 
 ○ “24-Hour; 5 Calendar Days” - The AE must initially be submitted electronically within 24 hours of learning of the AE, followed by a complete expedited report within 5 calendar days of the initial 24-hour report. ○ “10 Calendar Days” - A complete expedited report on the AE must be submitted electronically within 10 calendar days of learning of the AE. 		

¹Serious adverse events that occur more than 30 days after the last administration of investigational
		

agent/intervention and have an attribution of possible, probable, or definite require reporting as follows:

Expedited 24-hour notification followed by complete report within 5 calendar days for:

- All Grade 3, 4, and Grade 5 AEs

Expedited 10 calendar day reports for:

- Grade 2 AEs resulting in hospitalization or prolongation of hospitalization

²For studies using PET or SPECT IND agents, the AE reporting period is limited to 10 radioactive half-lives, rounded UP to the nearest whole day, after the agent/intervention was last administered. Footnote "1" above applies after this reporting period.

Effective Date: May 5, 2011

7.4.4 Additional Protocol-Specific Expedited Adverse Event Reporting Exclusions

For this protocol only, the AEs/grades listed below do not require expedited reporting via CTEP-AERS. However, they still must be reported through the routine reporting mechanism (Section 7.4):

- Any grade 1 or grade 2 laboratory abnormality that resolves within 7 days. Any grade 1 or grade 2 laboratory abnormality lasting for more than 7 days without resolution will require Expedited Adverse Event Reporting.
- Any grade 1 or grade 2 adverse event attributed as not related to study treatment.
- Any grade 1 or grade 2 adverse event attributed as possibly related or related to study treatment and is expected and resolves within 14 days. Any grade 1 or grade 2 adverse event attributed as possibly related or related to study treatment and is expected which does not resolve within 14 days will require Expedited Adverse Event Reporting.

7.5 **Routine Adverse Event Reporting**

All Adverse Events **must** be reported in routine study data submissions. **AEs reported expeditiously through CTEP-AERS must also be reported in routine study data submissions.**

Adverse event data collection and reporting, which are required as part of every clinical trial, are done to ensure the safety of patients enrolled in the studies as well as those who will enroll in future studies using similar agents. AEs are reported in a routine manner at scheduled times during the trial using Medidata Rave. For this trial the Adverse Event CRF is used for routine AE reporting in Rave.

Clinician graded CTCAE is the AE safety standard. Patients will respond to PRO-CTCAE items in a manner to complement CTCAE reporting, but no real-time review nor protocol directed action will be taken. The patient reported data will be entered directly from the patient's device into the RAVE database and may be available for the review with routine AEs.

7.6 **Secondary Malignancy**

A *secondary malignancy* is a cancer caused by treatment for a previous malignancy (e.g.,

treatment with investigational agent/intervention, radiation or chemotherapy). A secondary malignancy is not considered a metastasis of the initial neoplasm.

CTEP requires all secondary malignancies that occur following treatment with an agent under an NCI IND/IDE be reported expeditiously via CTEP-AERS. Three options are available to describe the event:

- Leukemia secondary to oncology chemotherapy (e.g., acute myelocytic leukemia [AML])
- Myelodysplastic syndrome (MDS)
- Treatment-related secondary malignancy

Any malignancy possibly related to cancer treatment (including AML/MDS) should also be reported via the routine reporting mechanisms outlined in each protocol.

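### Section 7.4.4 contradicts itself, the 7.4.3 table and the SPEER on which Grade 1–2 events need an expedited report

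*Combined protocol and SAP*

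**What the plan says.** Section 7.4.4 is headed "Additional Protocol-Specific Expedited Adverse Event Reporting Exclusions" and opens by stating that "the AEs/grades listed below do not require expedited reporting via CTEP-AERS". Section 7.3 gives it the same role. Three bullets follow:

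- Bullet 1 exempts "Any grade 1 or grade 2 laboratory abnormality that resolves within 7 days", then adds: "Any grade 1 or grade 2 laboratory abnormality lasting for more than 7 days without resolution will require Expedited Adverse Event Reporting".
- Bullet 2 exempts "Any grade 1 or grade 2 adverse event attributed as not related to study treatment".
- Bullet 3 exempts related, expected Grade 1–2 events that resolve within 14 days, then requires an expedited report for those that do not.

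Three other rules cover the same events:

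- Section 7.4.3 obliges investigators to report "ANY Serious Adverse Events, whether or not they are considered related to the investigational agent(s)/intervention". Its table gives Grade 1–2 events with hospitalisation of 24 hours or more a 10-calendar-day report.
- In the row "Not resulting in Hospitalization ≥ 24 hrs", the same table marks Grade 1–2 events as not required. The note under it places exceptions for serious events in the SPEER and does not mention 7.4.4.
- Section 7.3 says that SPEER-listed events "should be reported through CTEP-AERS only if the grade is above the grade provided in the SPEER". In both agents' lists (Section 7.1.1) that grade is 2 for ALT, AST and fatigue, among others.

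**The concern.** A section that should only remove events from the expedited stream also adds some, and it removes some that another section makes mandatory. A site coordinator holding a Grade 1–2 event can reach opposite answers from different lines of Section 7, and nothing says which line governs.

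Safety and tolerability are primary objectives in both cohorts (Section 1.1), and Section 5.2 acknowledges that the combination with radiation has had little testing. What is at stake is whether the sponsor receives the same events, on the same timescale, from every site. The limb with the most serious consequence is the third one: a serious event (admission of 24 hours or more) can be read as exempt from expedited reporting because it is Grade 1–2 and judged unrelated.

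**Working it through.** No arithmetic beyond comparing durations is involved, and the plan states no figure to reproduce. The check applies each rule, on its literal words, to five concrete cases. The inputs are the 7.4.3 table and its note, the SPEER rule in 7.3 with the lists in 7.1.1, and the three bullets of 7.4.4. A dash means that the rule does not address the case.

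| Case | 7.4.3 table | SPEER | Bullet 1 | Bullet 2 | Bullet 3 |
|---|---|---|---|---|---|
| A. Related, expected Grade 2 ALT increase, 20 days, not hospitalised | Not required | Exempt | Required (20 > 7) | – | Required (20 > 14) |
| B. Related, expected Grade 2 fatigue, unresolved at 14 days, not hospitalised | Not required | Exempt | – | – | Required |
| C. Unrelated Grade 1–2 laboratory value, 10 days, not hospitalised | Not required | Depends on term | Required (10 > 7) | Exempt | – |
| D. Related, expected Grade 1–2 laboratory value, resolves day 10, not hospitalised | Not required | Depends on term | Required (10 > 7) | – | Exempt (10 ≤ 14) |
| E. Unrelated Grade 2 non-laboratory event, not a SPEER term, hospitalised 24 h or more | Required, 10 calendar days | – | – | Exempt | – |

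1. *Exclusions that add duties (A, B).* ALT, AST and fatigue are on both agents' SPEER lists at Grade 2, so these cases do not depend on how a term listed for only one agent is treated in the combination. The table and the SPEER say no report; 7.4.4 says report. Section 7.4.4 sets no deadline for these reports, and the table has none for non-hospitalised Grade 1–2 events.

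2. *Bullets against each other (C, D).* Bullet 1's requirement has no condition on attribution or expectedness, so it overlaps bullets 2 and 3. Every unrelated Grade 1–2 laboratory value lasting more than 7 days gets two answers. So does every related, expected one that lasts more than 7 days but resolves within 14. Giving 7.4.4 precedence over 7.4.3 does not help, because both answers come from 7.4.4.

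3. *Hospitalised, unrelated events (E).* Bullet 2 has no carve-out for seriousness; 7.4.3 requires the report whatever the attribution. This limb applies up to 30 days after the last administration. After that, the footnote to the 7.4.3 table asks only for events at least possibly related. The exemptions in bullets 1 and 3 also lack a seriousness carve-out.

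**The case against.** The strongest reply is that 7.4.4 is meant to override. It is labelled protocol-specific, it applies to this protocol only, and 7.3 points to it for exemptions beyond the SPEER. Since the table already asks for nothing on non-hospitalised Grade 1–2 events, a Grade 1–2 exclusion has work to do only on hospitalised ones. That is a plausible account of case E, which makes the third limb the most arguable of the three as a contradiction. But no text says so, the duty in 7.4.3 is expressly independent of attribution, and its note names only the SPEER for exceptions.

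Two further readings would harmonise the bullets. The persistence sentences may only mark where an exclusion ends and return the event to 7.4.3; or bullet 1 may be the specific rule for laboratory values, leaving bullets 2 and 3 for everything else. Either is reasonable, and neither is stated. They also lead to different places: for cases C and D the first ends in no report, while the second, with bullet 1 read literally, ends in a report.

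The limits on consequence stand. Grade 3–5 timelines are untouched. All adverse events still go to routine reporting (Section 7.5), with data due at least every two weeks (Section 12.2.2). No endpoint, sample size or stopping rule changes.

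A reader might go further and infer that nearly every Grade 1–2 laboratory value becomes reportable, because scheduled blood tests are four weeks apart (Section 10), and that expedited reports would swamp real signals. The documents do not support this. Section 6 calls for creatinine weekly at Grade 1 and every 2–3 days at Grade 2, and for liver tests about every 1–2 days at Grade 2. Grade 1 liver tests do stay on the protocol schedule, but 7.4.4 contains no presumption that an unrepeated value persists. Any count of extra reports would need an assumed rate of persistent values, which the documents do not give.

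Nor is the attribution level Unlikely, which bullets 2 and 3 do not clearly place, a further contradiction. It is a gap: a non-laboratory event so classified falls back on the 7.4.3 table.

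**Conclusion.** The contradiction is real on the face of the text and has three parts: 7.4.4 requires what 7.4.3 and the SPEER do not; its own bullets give opposite answers for the same laboratory event; and bullet 2 exempts hospitalised, unrelated Grade 1–2 events that 7.4.3 makes mandatory. Sites following different lines will expedite different events.

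Its size is modest and cannot be expressed as a number of reports. It concerns the speed and consistency with which Grade 1–2 events reach the sponsor, not whether they are recorded. The conclusion rests on the literal wording and on the absence of any precedence rule in Section 7; a written statement of precedence together with non-overlapping bullets would dispose of it. Because it is a contradictory safety-reporting rule rather than a missing detail, and cheap to correct, it should be corrected.

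**What to change.** Reconcile 7.4.3, the SPEER and 7.4.4 in one amendment:

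- State which of the three prevails when they differ.
- Limit the 7.4.4 exclusions to non-serious events, so that Grade 1–2 events with hospitalisation of 24 hours or more stay on the 10-calendar-day report, SPEER exceptions aside.
- Make the bullets mutually exclusive, and word them with the five attribution terms of Section 7.3 so that Unlikely has a place.
- Either delete the two persistence requirements or, if the sponsor deliberately wants persistent Grade 1–2 events expedited, state that requirement consistently in 7.4.3 and the SPEER note, with one duration clock and a deadline.

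The cost is a few lines of protocol text and a note to sites. The correction itself needs no new data or procedures.
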